9.2 Sample Size Determination

This study is anticipated to screen up to 75 subjects to enroll approximately 60 subjects coinfected with HIV and HBV, who are currently on antiretroviral therapy. The primary analysis endpoint to evaluate treatment efficacy used to compute the sample size is the observed HIV-1 viral suppression rate. A true suppression rate at Week 24 of at least 91% would be considered active in this patient population. An exact binomial test with a 0.05 type I error rate will have 84% power to detect the difference between the null hypothesis proportion (number of suppressed/total number treated) of 0.773 (based on published results) and the research hypothesis proportion of 0.910 (our educated guess on the desired rate of success) when the sample size is 60.

9.2.1 Analysis Objectives

The primary objective of this study is to evaluate the efficacy of FDC B/F/TAF in adults coinfected with both HIV-1 and HBV, after switching from their current antiretroviral regimen, as determined by HIV-1 RNA <50 copies/mL and/or HBV DNA <29 IU/mL at Week 24.

The secondary objectives of the study include evaluation of HIV-1 and HBV viral suppression at Week 48 as well as safety and tolerability at Week 24 and Week 48.

9.2.2 Analysis of the Primary Efficacy Endpoints

The primary endpoints are:

- The proportion of subjects with HIV-1 RNA <50 copies/mL at Week 24 as defined by the US FDA Snapshot Algorithm.
- The proportion of subjects with plasma HBV DNA <29 IU/mL at Week 24 using the missing = failure method.

9.2.2.1 US FDA Snapshot Algorithm for HIV-1 Efficacy Analyses

The analysis window at Week 24 is defined as from Study Day 140 to Day 196. All HIV-1 RNA data collected on-treatment will be used in the snapshot algorithm. HIV-1 Virologic outcome will be defined as the following categories:

- **HIV-1 Virologic Success:** this includes subject who have the last available HIV-1 RNA < 50 copies/mL in the Week 24 analysis window while on study treatment.
- **HIV-1 Virologic Failure:** this includes subjects who
 - a. Have the last available HIV-1 RNA \geq 50 copies/mL in the Week 24 analysis window while on study treatment, or
 - b. Do not have on-treatment HIV-1 RNA data in the Week 24 analysis window and
 - 1) Discontinue study drug prior to or in the Week 24 analysis window due to lack of efficacy, or
 - 2) Discontinue study drug prior to or in the Week 24 analysis window due to reasons other than adverse events (AE), death, or lack of efficacy and have the last available HIV-1 RNA up to 1 day after the premature discontinuation of the study drug \geq 50 copies/mL.
- **No HIV-1 Virologic Data in the Week 24 analysis window:** this includes subjects who do not have on-treatment HIV-1 RNA data in the Week 24 analysis window because of the following:
 - a. Discontinuation of the study drug prior to or in the Week 24 analysis window due to AE or death (regardless of whether the last available HIV-1 RNA up to 1 day after the premature discontinuation of the study drug < 50 copies/mL or not), or
 - b. Discontinuation of the study drug prior to or in the Week 24 analysis window due to reasons other than AE, death, or lack of efficacy (e.g., withdrew consent and loss to follow-up) and the last available HIV-1 RNA up to 1 day after the premature discontinuation of the study drug is < 50 copies/mL, or
 - c. Missing data during the window but remains on study drug.

9.2.2.2 Missing = Failure Method for HBV Efficacy Analyses

Similarly, the analysis window at Week 24 for HBV DNA outcomes is defined as from Study Day 140 to Day 196. For HBV DNA analysis, this study will use the missing = failure method. HBV virologic outcome will be defined as follows:

- **HBV Virologic Success:** this includes subject who have the last available HBV DNA <29 IU/mL in the Week 24 analysis window while on study treatment.
- **HBV Virologic Failure:** this includes subjects who
 - a. Have the last available HBV DNA \geq 29 IU/mL in the Week 24 analysis window while on study treatment, or
 - b. Do not have on-treatment HBV DNA data in the Week 24 analysis window regardless of reason (e.g. discontinued study drug due to AE, death or lack of efficacy; missed Week 24 visit; withdrew consent for any reason).

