1.1.1 Tenofovir alafenamide in HIV-HBV Coinfection

Tenofovir, in the form of tenofovir disoproxil fumarate (TDF) has been one of the mainstay agents for the treatment of chronic HBV infection. Tenofovir disoproxil fumarate has demonstrated potency and predictable high long-term efficacy resulting in sustained HBV viral suppression with favorable safety profile ([EASL 2017](#)). The durability of tenofovir based therapy has been well documented with published data as long as 7-years showing 99.3% of patients (N=427) taking TDF maintaining viral suppression. In this publication by [name] and colleagues, 80% had ALT normalization, and close to 12% of HBeAg-positive chronic HBV subjects had HBsAg loss ([Buti M et al. 2015](#)). Long-term therapy with TDF was also associated

with regression of fibrosis in up to 80% by year 5 ([Marcellin P et al. 2013](#)). In addition, no resistance to TDF was detected in these multi-year studies ([Buti M et al. 2015](#)). The lack of resistance-associated variants (RAV) developing during TDF therapy has been thought to be related to several possible factors including: (1) the high binding affinity of tenofovir to YMDD (the HBV reverse transcriptase target); (2) higher (30 times) dosage of the tenofovir (compared to other anti-HBV drugs such as adefovir); and (3) the constrained mutational space due to gene overlap in HBV genome ([Van Hemert et al. 2014](#)).

Tenofovir alafenamide (TAF) is a phosphonated prodrug of tenofovir, developed by Gilead Sciences, due to its enhanced plasma stability compared to TDF. This allows higher levels of the active intracellular form of tenofovir diphosphate to concentrate in target cells such as the hepatocytes and lymphoid cells, for the treatment of HBV and HIV-1, respectively ([Mukurami E et al 2013; Birkus G et al. 2012](#)). As it is able to remain mostly intact in the plasma, TAF administration is associated with reduced systemic tenofovir exposure compared to TDF, resulting in corresponding reduction in renal or bone complications ([Agarwal K et al. 2015](#)).

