1.2 Bictegravir/Emtricitabine/Tenofovir Alafenamide (B/F/TAF)

1.2.1 Description

Bictegravir/emtricitabine/tenofovir alafenamide is FDA-approved (approval date February 2018) fixed dose combination drug regimen under the brand name BIKTARVY® (Gilead Sciences Inc.). It is indicated as a complete regimen for the treatment of HIV-1 infection in adults who have no antiretroviral treatment history or to replace the current antiretroviral regimen in those who are virologically suppressed (i.e. HIV-1 RNA <50 copies/mL) on a stable antiretroviral regimen ([Biktarvy 2018](#)). Bictegravir/emtricitabine/tenofovir alafenamide contains an HIV-1 integrase strand transfer inhibitor, bictegravir, and two HIV-1 nucleos(t)ide analog reverse transcriptase inhibitors, tenofovir alafenamide (TAF) and emtricitabine (FTC). Both TAF and FTC have activity against HBV infection. B/F/TAF is a complete regimen that has the potential to offer HIV-HBV coinfecting patients a simple, once daily regimen containing drug components that provides a high barrier to resistance against both HIV-1 and HBV. B/F/TAF does not require boosting, and potentially offers an effective and safe alternative to other regimens, without need for human leukocyte antigen (HLA) testing or close monitoring of renal or bone toxicities.

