3.2.8 Virologic Failure

HIV-1 virologic failure is defined as virologic rebound or having HIV-1 RNA ≥ 50 copies/mL at study drug discontinuation, Week 24, or Week 48.

HBV virologic failure is defined as virologic rebound or having HBV DNA ≥ 29 IU/mL at study drug discontinuation, Week 24, or Week 48. Development of tenofovir resistance plus use of an anti-HBV agent (e.g. entecavir) other than the study drug during the treatment period will also be considered a HBV virologic failure.

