Following unconfirmed virologic rebound, subjects will be asked to return to the clinic for a scheduled or unscheduled blood draw (2 to 3 weeks after the date of the original test that resulted in HBV DNA virologic rebound) for confirmation of virologic rebound. If virologic rebound is confirmed at the scheduled or unscheduled visit and the HBV DNA is ≥500 IU/mL, the blood sample from the confirmation test will be the primary sample used for HBV genotyping and drug resistance assay. Subjects with documented non-adherence within 72 hours of the visit may not be tested for resistance. After a subject's first postbaseline resistance test, additional testing will be conducted on a case-by-case basis. Any subject may be discontinued at Investigator's discretion.

[figure not shown]
If no resistance is detected, the subject may remain on study drug and a repeat HBV DNA should be repeated (approximately 2 to 3 weeks after date of latest test with HBV DNA ≥29

IU/mL). Investigator should carefully evaluate the benefits and risk of remaining on the study drug for each individual subject and document this assessment in the medical record.

Subject who are noncompliant on an ongoing basis will be considered for discontinuation per the Investigator's discretion.

For subjects who are off study drug but remain on study, it will be the Investigator's discretion to manage virologic rebound.

Figure 6-2 illustrates the algorithm for the management of subjects who meet the criteria for HBV virologic rebound.

*Addition of a “3rd” HBV agent in the setting of tenofovir resistance is considered a HBV virologic failure.

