9 STATISTICAL CONSIDERATIONS

9.1 General Consideration & Populations for Analyses

The primary analysis for efficacy analyses will employ intention-to-treat (ITT) population defined as the full analysis population, which will include all subjects who have received at least 1 dose of the study drug.

The secondary analysis for efficacy analyses will employ a per-protocol (PP) population, which will include all subjects who have received at least one dose of the study drug, and have not committed any major protocol violation, including the violation of key eligibility criteria. In the Week 24 (or Week 48) per-protocol analysis, subjects meeting any of the following criteria will be excluded:

- a. Subjects who do not have on-treatment HIV-1 RNA and/or HBV DNA in the Week 24 (or Week 48) analysis window, except when missing data is due to discontinuation of study drug for lack of efficacy.
- b. Subjects who were removed from study due to nonadherence to study drug or due to protocol violation by the subject.

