9.2.3 Analysis of the Secondary Endpoints

The secondary endpoints include:

- The proportion of subjects with HIV-1 RNA < 50 copies/mL at Week 48 as defined by the US FDA Snapshot Algorithm.
- The proportion of subjects with plasma HBV DNA < 29 IU/mL at Week 48 using the missing = failure method.
- Change from baseline in CD4 cell count and percentage at Week 24 and at 48.
- Proportion of subjects with normalized ALT at Week 24 and Week 48.
- Proportion of subjects with HBV e antigen (HBeAg) loss and seroconversion to anti-HBe at Week 24 and Week 48.
- Proportion of subjects with HBV surface antigen (HBsAg) loss and seroconversion to anti-HBs at Week 24 and Week 48.
- Change from baseline in Fibroscan test score at Week 24 and Week 48.

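### Sections 3.2.8/3.2.9 and 9.2.2.2 define HBV virologic failure differently, so a subject whom the protocol calls an HBV failure can be scored a success at Week 24 and Week 48

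*Combined protocol and SAP*

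**What the plan says.** **Endpoint definition.** Section 9.2.2.2 presents its categories as the definition of HBV outcome. Success is: "this includes subject who have the last available HBV DNA <29 IU/mL in the Week 24 analysis window while on study treatment". There are two ways to fail: a last in-window, on-treatment HBV DNA at or above 29 IU/mL, or no on-treatment value in the window (Day 140 to Day 196) for any reason. The section mentions neither resistance, nor added anti-HBV drugs, nor rebound, and it does not refer to 3.2.8.

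**Failure label in the investigational plan.** Section 3.2.8 counts as HBV virologic failure a virologic rebound, or an HBV DNA at or above 29 IU/mL at drug discontinuation, Week 24 or Week 48. It then adds one more category: "Development of tenofovir resistance plus use of an anti-HBV agent (e.g. entecavir) other than the study drug during the treatment period". The note to the HBV algorithm in 3.2.9 repeats it, saying that adding a third "HBV agent in the setting of tenofovir resistance is considered a HBV virologic failure".

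**Week 48.** Section 9.2.3 carries the same method forward: "The proportion of subjects with plasma HBV DNA < 29 IU/mL at Week 48 using the missing = failure method". It gives no separate outcome rule.

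**Per-protocol set.** The listed exclusions in 9.1 are subjects without on-treatment viral data in the window (unless the data are missing because drug was stopped for lack of efficacy) and "Subjects who were removed from study due to nonadherence to study drug or due to protocol violation by the subject". Neither names a subject who was given another anti-HBV drug.

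**The concern.** Both sections use the same term, the same 29 IU/mL threshold and the same visits, yet they can classify one subject in opposite ways. The added-drug case matters most. If another anti-HBV agent brings HBV DNA below 29 IU/mL, the primary HBV endpoint would credit that result to B/F/TAF, against the protocol's own classification. The rebound case is different in kind, because a subject who re-suppresses on B/F/TAF alone has not been rescued by another drug. The conflict between the two definitions is still there.

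The trial is open-label and single-arm. If the rule is left open, the choice between the two definitions would be made with the subject's result already known.

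**Working it through.** **1. The plan's only power figure.** Section 9.2 states 84% power for the HIV-1 endpoint (n = 60, null 0.773, alternative 0.910, type I error 0.05). The smallest r with P(X ≥ r | 60, 0.773) ≤ 0.05 is r = 53, where the exact error is 0.0237; r = 52 gives 0.0514. Power is P(X ≥ 53 | 60, 0.910) = 83.1%, close to the stated figure. HBV outcome does not enter this calculation. No null rate, test or power is stated for HBV.

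**2. Classification side by side.** In each row the last in-window HBV DNA is below 29 IU/mL, except where no on-treatment value exists.

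| Subject | 3.2.8 / 3.2.9 | 9.2.2.2 |
|---|---|---|
| Resistance, other agent added, still on study drug | Failure | Success |
| Earlier confirmed rebound, re-suppressed, still on study drug | Failure | Success |
| Resistance, other agent added, no on-treatment value in window | Failure | Failure (category b) |

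**3. Does study drug continue?** For rebound the text answers this: 3.2.9 allows a subject with no detected resistance to stay on study drug. For the added-drug case it is an inference. The 3.2.9 note counts the added drug as the third HBV agent, and 1.2.1 says "Both TAF and FTC have activity against HBV infection". A third agent therefore suggests that the first two continue.

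**4. Does timing allow it?** Resistance is assessed after rebound is confirmed: "the blood sample from the confirmation test will be the primary sample used for HBV genotyping and drug resistance assay". The confirmatory draw comes 2 to 3 weeks after the first result, and the assay needs HBV DNA of at least 500 IU/mL. Taking week w as Day 7w (which agrees with 168 ± 28 = Day 140 to 196):

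- Week 12 rebound: Day 84, confirmed Day 98 to 105. To nominal Week 24 (Day 168): 168 − 105 = 63 to 168 − 98 = 70 days. To the end of the window (Day 196): 91 to 98 days.
- Week 36 rebound: Day 252, confirmed Day 266 to 273. To nominal Week 48 (Day 336): 336 − 273 = 63 to 336 − 266 = 70 days.

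Assay turnaround is not given and would shorten these intervals. Timing does not rule the case out.

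**5. Size per subject.** 1/60 = 1.67 points. The illustration below assumes 55 successes of 60 under 9.2.2.2. The exact 95% limits are the 0.025 quantile of Beta(y, 61 − y) and the 0.975 quantile of Beta(y + 1, 60 − y).

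| Rescored | y/60 | Proportion | Exact 95% CI |
|---|---|---|---|
| 0 | 55/60 | 91.7% | 81.6 to 97.2 |
| 1 | 54/60 | 90.0% | 79.5 to 96.2 |
| 2 | 53/60 | 88.3% | 77.4 to 95.2 |
| 3 | 52/60 | 86.7% | 75.4 to 94.1 |

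**6. How many?** The documents give no expected count for either event. On resistance, 1.1.1 reports that "no resistance to TDF was detected in these multi-year studies", so zero added-drug cases is plausible.

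**The case against.** **The protocol already classifies these subjects.** Section 3.2.8 names Week 24 and Week 48, and the failure list in 9.2.2.2 opens with wording that could be read as inclusive, so 3.2.8 might simply supply further members. This reading is possible, but 9.2.2.2 also presents itself as the definition and its success rule has no exception. The text is ambiguous, which is enough to require a sentence.

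**Section 3.2.8 may be a separate label.** If it serves only the investigational plan, neither extra category belongs in the endpoint, and importing one while ignoring the other would be arbitrary. That is fair, and it is why both categories have to be addressed. The document does not say that 3.2.8 is separate.

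**The subject may be off study drug.** Permission to remain on drug is visible only where no resistance is detected, and lack of efficacy is a listed reason to stop. This stands as a condition on the added-drug case. It does not affect the rebound case.

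**It will rarely happen.** This also stands. A reader might infer a sizeable chance of at least one misclassified subject by setting a bound on resistance from the N = 427 in 1.1.1. The documents do not support that. The 427 is given for maintained suppression on TDF, the data run to as long as 7 years rather than 24 or 48 weeks, and resistance is only the first step. A misclassification also needs resistance to be detected, another drug to be added, study drug to continue, and HBV DNA to return below 29 IU/mL in the window.

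**Conclusion.** The two definitions conflict and should be reconciled before analysis. The point is minor. Its effect is 1.67 points on the reported HBV proportion per subject at N = 60, with few or no added-drug cases expected and no rebound frequency given. The Week 48 part rests on 9.2.3 using the same method. The added-drug part rests on study drug continuing, which cannot be confirmed without Figure 6-2.

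A reader might infer that every subject with tenofovir resistance would be counted as a B/F/TAF success. The documents do not support that, because a subject with no on-treatment value in the window, or with a last value at or above 29 IU/mL, is already a failure under 9.2.2.2. Nor does the point reach the HIV-1 test or its power. It gives no reason to depart from the Snapshot last-value rule for HIV-1.

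**What to change.** 1. Add to 9.2.2.2 that a subject who meets the existing 3.2.8 resistance-plus-other-agent category before or in the analysis window is an HBV failure whatever the HBV DNA.
2. Apply the same sentence to the Week 48 HBV endpoint in 9.2.3.
3. State whether the 3.2.8 rebound category also counts as failure for the HBV endpoint or is a separate label. If it is separate, say what the label is used for and tabulate the Week 24 and Week 48 HBV successes that had an earlier confirmed rebound.

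The cost is a few sentences in section 9.2. The data are already collected: concomitant medication at every visit, HBV DNA at every visit, and the resistance assay where its threshold is met. Because that assay is conditional, the first category can be applied only to subjects who were tested. The downside is that the reported HBV rate may be slightly lower. Sample size and power do not change, and no change to retesting, rescue or other clinical management is proposed.

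### Sections 3.2.8/3.2.9 and 9.2.2.2 define HBV virologic failure differently, so a subject with tenofovir resistance who is suppressed on B/F/TAF plus an added anti-HBV agent could be scored either way

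*Combined protocol and SAP*

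**What the plan says.** **Analysis section.** Section 9.2.2.2 sets out the HBV outcome categories for the Week 24 window, Day 140 to Day 196. For success, "this includes subject who have the last available HBV DNA <29 IU/mL in the Week 24 analysis window while on study treatment". Failure has two limbs: (a) a last in-window on-treatment HBV DNA of 29 IU/mL or more, and (b) subjects who "Do not have on-treatment HBV DNA data in the Week 24 analysis window regardless of reason". Neither limb mentions resistance or added HBV therapy, and Section 3.2.8 is not cited. Section 9.2.3 carries the method to the secondary endpoint, the proportion below 29 "IU/mL at Week 48 using the missing = failure method", without a separate failure list.

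**Procedures section.** Section 3.2.8 begins: "HBV virologic failure is defined as virologic rebound or having HBV DNA" at or above 29 IU/mL when study drug is stopped or at either endpoint week. It then makes a further case a failure: "Development of tenofovir resistance plus use of an anti-HBV agent (e.g. entecavir) other than the study drug" during treatment. A footnote in Section 3.2.9 repeats the rule: adding a third "HBV agent in the setting of tenofovir resistance is considered a HBV virologic failure".

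**Management after rebound.** The readable text of Section 3.2.9 covers one branch only: "If no resistance is detected, the subject may remain on study drug and a repeat HBV DNA should be repeated". For the rest, "Figure 6-2 illustrates the algorithm for the management of subjects who meet the criteria for HBV virologic rebound"; that figure is not reproduced in the text available for review.

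**The concern.** The same term, HBV virologic failure, is defined in two places, and the definitions can give opposite answers for one subject on a primary endpoint. If Section 9.2.2.2 is followed literally, suppression reached with the help of a rescue agent is credited to B/F/TAF, although the protocol elsewhere calls that outcome a failure. The trial is open-label with a single arm (Sections 6.2 and 6.5), so the choice between the two rules should not be left until results are known. The Week 24 primary and Week 48 secondary HBV proportions are both exposed.

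**Working it through.** **1. The plan's own figure.** Section 9.2 states 84% power for an exact binomial test with N = 60, null 0.773, alternative 0.910 and type I error 0.05. With X ~ Bin(60, p):

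- P(X ≥ 52 | 0.773) = 0.0514, which exceeds 0.05.
- P(X ≥ 53 | 0.773) = 0.0237, so the cutoff is 53/60.
- Power = P(X ≥ 53 | 0.910) = 0.831, within one point of the stated 84%.

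This calculation is for HIV-1 suppression. The plan states no HBV hypothesis or HBV power, so nothing below changes it.

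**2. The two rules applied to one subject.** Take a subject with tenofovir resistance on treatment, entecavir added, B/F/TAF continued, and last HBV DNA in Day 140–196 below 29 IU/mL.

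| Rule | Met? | Class |
|---|---|---|
| 9.2.2.2 success (below 29, on study treatment) | Yes | Success |
| 9.2.2.2 failure (a), 29 or more | No | – |
| 9.2.2.2 failure (b), no on-treatment value | No | – |
| 3.2.8, resistance plus another agent | Yes | Failure |
| 3.2.9 footnote, third agent | Yes | Failure |

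The on-treatment condition does not remove the conflict if B/F/TAF continues. Continuation is an inference. B/F/TAF already contains two HBV-active drugs, TAF and FTC (Section 1.2.1), so a third agent suggests one added on top of them.

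**3. Whether another section settles it.** The two listed per-protocol exclusions in Section 9.1 do not name this case. That section also excludes major protocol violations without itemising them, so it does not show whether the subject would be removed or kept. Table 6-1 in Section 6.6 lists no anti-HBV agent as prohibited.

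**4. Whether there is time for it to happen.** A rebound at Week 12 (7 × 12 = Day 84), confirmed three weeks later, gives 84 + 21 = Day 105. That leaves 140 − 105 = 35 days to window opening and 196 − 105 = 91 days to window close. Assay turnaround and the start of the new agent must fit within that time. Week 48 allows more.

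**5. Size.** With 60 subjects dosed, each reclassified subject moves the proportion by 1/60 = 1.67 points, and two move it by 2/60 = 3.33. The documents give no rate of such events in this trial, so the range of 0 to 2 subjects and the starting counts below are assumptions. Exact (Clopper–Pearson) 95% limits are the 0.025 quantile of Beta(x, n − x + 1) and the 0.975 quantile of Beta(x + 1, n − x).

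| Subjects reclassified | From 57/60 | From 55/60 |
|---|---|---|
| 0 | 95.0% (86.1–99.0) | 91.7% (81.6–97.2) |
| 1 | 93.3% (83.8–98.2) | 90.0% (79.5–96.2) |
| 2 | 91.7% (81.6–97.2) | 88.3% (77.4–95.2) |

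**The case against.** The best reply is that the protocol already contains the rule. Section 3.2.8 states it, ties failure to the endpoint weeks, and uses the same term as Section 9.2.2.2. An analyst who reads the whole document could score the subject as a failure, which would leave only a missing cross-reference. Part of this stands: the failure scoring is an available reading. But Section 9.2.2.2 presents itself as the definition of the outcome, and applied literally it gives the opposite class. A missing pointer would not produce that contradiction.

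A second reply is that the case depends on a branch that cannot be read. If Figure 6-2 stops study drug when resistance is found, and no on-treatment value falls in the window, limb (b) already makes the subject a failure. This stands as a condition on the finding. The third-agent footnote points towards continuation but does not prove it.

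A third reply is rarity, and it stands in full. The route needs a confirmed rebound, HBV DNA of at least 500 IU/mL for the resistance assay, resistance detected, an agent added, B/F/TAF continued, and re-suppression by Day 196. Section 1.1.1 reports that long-term TDF studies found no resistance.

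A reader might also infer that scoring a confirmed rebound that later re-suppresses as a success is an error of the same kind, since Section 3.2.8 counts rebound as failure. The documents do not support that. The endpoint in Section 2.4 is a proportion at a fixed time point, and the HIV-1 rules in Sections 3.2.8 and 9.2.2.1 have the same structure. A last-value-in-window endpoint is defensible; the protocol only needs to say which rule governs.

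**Conclusion.** The conflict between Sections 3.2.8/3.2.9 and 9.2.2.2 is real and should be corrected before analysis. It is minor: 1.67 points on the HBV proportion per affected subject if 60 are dosed, with an expected number near zero and possibly none. No HBV test or power depends on it, and the HIV-1 sample-size calculation is untouched.

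A reader might go further and infer that a rescued subject certainly counts as a Week 24 success, or that the reported HBV rate will be inflated. Neither follows. The first depends on the resistance branch of Figure 6-2, which is not shown, and on choosing the literal reading of Section 9.2.2.2. The second needs at least one such subject, and the documents give no reason to expect any. The 57/60 and 55/60 starting points are illustrations only.

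**What to change.** **In Section 9.2.2.2**, add a third limb to HBV Virologic Failure and apply it at Week 48 as well:

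> c. develops tenofovir resistance and receives an anti-HBV agent other than study drug before or in the analysis window, whatever the in-window HBV DNA.

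**In Section 3.2.8**, add a sentence saying that confirmed rebound guides clinical management, and that the Week 24 and Week 48 endpoints are scored only by Sections 9.2.2.1 and 9.2.2.2 as amended.

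The rescue rule moves into the endpoint and the rebound rule does not, for a reason. Suppression reached with another HBV drug cannot be attributed to B/F/TAF alone. A rebound that re-suppresses on B/F/TAF alone is a valid outcome for the fixed time-point endpoint that the protocol states. The HIV-1 rebound criteria need no change.

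The cost is one list item and one sentence. Concomitant medications are recorded at every visit (Appendix A) and HBV resistance testing is already planned (Section 3.2.9 and Appendix A), so no new data, visits or subjects are needed.
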